Phase II: 20 additional subjects with post-COVID-19 infection coming to the COVID-19 clinic at Baylor College of Medicine for treatment of complications (i.e., hospital acquired weakness due to neuromyopathy). Patients will begin the study after being diagnosed with neuromyopathy due to prolonged hospitalization for COVID-19. This will be performed by a critical care and pulmonary specialist at the BCM COVID-19 Clinic. The entire cohort will receive daily electrical stimulation in lower extremity (e.g. Gastrocnemius, tibial anterior muscle) up to 1 hour to recover from Neuromyopathy complications and prolonged hospital stay. The patients will take the device home up to 4 weeks and will be screened once a week at the COVID-19 clinic for neuromuscular evaluation.

Inclusion Criteria:

Age: Adults age 18 years or older Disease status: COVID-19 test positive Critically ill requiring care in the hospital.

Patients must have been previously hospitalized due to COVID-19 infection and diagnosed with hospital acquired weakness by pulmonary care specialists. Patients will have to be alert and conscious to sign the consent form.

Exclusion Criteria:

Subject has a demand-type cardiac pacemaker, implanted defibrillator or other implanted electronic device Active wound infection Below the knee amputations Based on the clinicians decision whether the patient is eligible for the study.

F2. Procedure

Phase I:

Aim1 (to understand mechanism of action): Examine immediate benefit of lower extremity EE to improve venous return flow, tissue oxygenation, and muscle activation (short term benefit). In this study, we will recruit a convenient sample of 20 hospital patients diagnosed with COVID-19 (short-term benefit).

Optional: Subjects will be assessed using Doppler ultrasound and near infrared imaging (Kent Imaging System) at pre-, 30min, 60min, and 30min post-treatment (after stopping of EE device). Lower extremity muscle activation will be assessed by using sEMG (electromyography).

Patients will begin the study after being admitted to the hospital no more than 48 hours.

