Aim 2 (to examine effectiveness): Examine effectiveness of daily use of EE to treat CINM, and other associated major adverse events (MAE) including deep vein thrombosis (DVT), cardiovascular events, and death. Participants will receive standard of care plus adjunctive daily EE therapy using an FDA approved bio-electric stimulation technology (BEST) platform (Tennant Biomodulator® PRO, AVAZZI A, Inc) during the entire length of stay in hospital. The device will be provided by the research staff.

We will assess incidence of neuropathy and myopathy during hospital discharge or 4 weeks, whichever comes first. Neuropathy severity will be quantified using vibratory perception threshold (VPT) test. Myopathy will be assessed by measuring changes in calf muscle circumference, weight change from pre-hospital admission, and sEMG. In addition, we will determine weakness using foot dynamometer and a validated frailty meter. Length of hospital stay and MAE (documented via electronic health record) will be tracked for planning of future studies. Both extremities will have all measurements and 1 hour electrical stimulation therapy at baseline. Daily treatment will be performed up to 3 times per day, but no more than 1 hour in total.

Daily electrical stimulation will be administered by a nurse/staff involved in the hospital care. A chart will be signed to register each therapy performed and will include a log of day and time of device application.

Both electrical stimulation and EMG devices will have disposable pads, after usage they will be discarded. For the Devices

they will be placed inside a plastic bag that will be disposed inside the room before exiting and sanitized (wipes) based upon hospital protocols.

The researchers will take digital photographs /videos throughout the study. This is done using a special camera for tissue oxygen detection and visual images. This method is non invasive and does not cause any harm to the patient. **We will blur the face out in the photographs/videos. We will only use videos and photos for scientific presentations or scientific publications.

Phase II:

Patients will begin the study after being diagnosed with neuromyopathy due to prolonged hospitalization for COVID-19. This will be performed by a critical care and pulmonary specialist at the BCM COVID-19 Clinic.

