Describe potential benefit(s) to be gained by the individual subject as a result of participating in the planned work.

There is potential benefit of prevention or improvement of hospital acquired weakness due to prolonged hospital stay for participants, based on previous studies the electrical stimulation will improve blood flow, tissue perfusion and muscle activation. The device is used to reduce pain. However, the proposed treatment may assist in preventing or improving hospital-acquired Weakness because of prolonged hospital stay . In addition, the participation in this study may help the investigators better understand how COVID19 may impact cause myopathy and neuropathy and how to best help these patients to recover from prolonged hospital-stay .

Primary outcomes include neuropathy (assessed using VPT test); muscle function (assessed using sEMG), and tissue oxygenation (assessed using Kent Imaging). Secondary outcomes include weakness (assessed using dynamometer); muscle atrophy (assessed by weight loss as well as measuring ankle, calf, and thigh circumference); venous return flow (Doppler US [optional]); frailty (frailtymeter [optional]); hospital length of stay (patient medical record); and major adverse events (patient health record). The primary and secondary outcomes will be assessed at baseline (if feasible) and on biweekly basis up to 4 weeks or hospital discharge, whichever came first. Appropriate mixed models (linear for continuous or Generalized Estimating Equations (GEEs) for non-continuous or non-parametric variables) will be used to test the intervention effect for each of the primary (e.g., tissue perfusion, tissue oxygen delivery, neuropathy severity, and

myopathy incident) or secondary (e.g., frailty, weight loss, MAE, etc) outcomes.

Also, participation may help the investigators design a practical assessing method to identify the impact of neuromyopathy in the hospital setting. This may allow physicians to provide personalized care by monitoring muscle loss and limb complications caused by prolonged hospital length of stay.

Describe potential benefit(s) to society of the planned work.

As described above, this type of work may allow physicians to provide more personalized care for hospitalized patients in need of physical therapy for continuous and prolonged periods, specially when having a severe illness that includes medical staff risk contact.

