Title: Electrical Stimulation Therapy for Preventing Hospital-acquired Weakness in Critically Ill COVID-19 Patients - A Proof of Concept Randomized Controlled Trial

Identifier: NCT04685213

Date: May 21, 2021

Statistical analysis plan

Shapiro-Wilk test ($p > 0.05$) was used to assess the normality of data. Independent t-test was used for group comparison at baseline on normally distributed continuous demographics, clinical data, and sEMG parameters. Mann-Whitney U test was used if the assumption of normal distribution was not satisfied. For categorical variables, Chi-square test was used to compare between-group differences at baseline. The effect size for baseline continuous and categorical data were measured using Cramer's V and Cohen's d, respectively. Generalized estimating equations (GEE) was used to test the main effect of group (two levels: CG and IG), time (three levels: baseline, 3 days, and 9 days), and their interaction on the outcome measures regardless of data unable to obtain due to the patients' critical condition. Pearson correlation was used to associate baseline values with %change of outcomes at 9 days. For those significant associations, multiple linear regression was used to determine the relationship between those significantly associated variables. The model performance was reported in terms of variance (R^2), and p-value. For all tests, an alpha level of < 0.05 was considered statistically significant.

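### In-hospital sEMG, tissue oxygenation, Doppler and possibly strength readings are not timed relative to stimulation sessions, so an immediate device effect may be counted as prevention or treatment of neuromyopathy

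*Protocol*

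**What the plan says.** **Outcome schedule.** Section I of the protocol names three primary outcomes: neuropathy by VPT, muscle function by sEMG, and tissue oxygenation by Kent Imaging. On timing it says "The primary and secondary outcomes will be assessed at baseline (if feasible) and on biweekly basis", until four weeks or discharge. The SAP models "time (three levels: baseline, 3 days, and 9 days". Neither gives a time of day or an interval from the last session.

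**Treatment during follow-up.** Under Aim 2 (Section F2, Phase I) stimulation is given "during the entire length of stay in hospital". The same section states "Daily treatment will be performed up to 3 times per day, but no more than 1 hour in total". A patient still in hospital is therefore assessed on a treatment day, and that day may hold one, two or three sessions.

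**Expected acute effect.** Aim 1 is to "Examine immediate benefit of lower extremity EE to improve venous return flow, tissue oxygenation, and muscle activation (short term benefit". Its Doppler and near-infrared readings are scheduled "at pre-, 30min, 60min, and 30min post-treatment (after stopping of EE device". They are optional, have no stated study day and are not linked to the SAP time points. sEMG is to assess muscle activation under this aim, with no clock times.

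**Baseline.** Aim 2 places all measurements and one hour of stimulation at baseline without giving their order.

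**Comparison.** The SAP fits GEE with "group (two levels: CG and IG", time and their interaction, in a trial titled as "Preventing Hospital-acquired Weakness in Critically Ill COVID-19 Patients". Section F1 of the protocol instead describes Phase I as one cohort of 20, all stimulated.

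**Session record.** A therapy chart logs the day and time of each application. No stated analysis uses it.

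**The concern.** The protocol separates two questions. Aim 1 asks whether stimulation changes flow, oxygenation and muscle activation while the device runs and shortly afterwards. Aim 2 asks whether daily use treats critical illness neuromyopathy. sEMG and oxygenation, two of the three primary outcomes, measure quantities that Aim 1 expects to move within an hour. If a follow-up reading may fall during, just after or hours after a session, the Aim 2 result contains an unknown amount of the Aim 1 effect.

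A control group does not remove it. Only stimulated patients can carry the acute effect, so it enters the group and group-by-time terms directly, and an inactive device would not change that. In the single-cohort version it enters the change from baseline. What is at stake is the interpretation of sEMG and oxygenation: better readings could be taken as preserved muscle or perfusion when they partly show a recent session.

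**Working it through.** **1. Is reading time fixed anywhere?** No. Section I and the SAP give calendar schedules only. The session-linked readings under Aim 1 are optional and separate. The GEE has no term for time since stimulation.

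**2. Which outcomes are exposed?**
- Exposed, because Aim 1 names the quantity: sEMG, tissue oxygenation, Doppler flow.
- Possibly exposed: dynamometer strength, through muscle activation or, in the other direction, fatigue (Section H1 expects the EMG to detect fatigue and to inform session length).
- Not named by Aim 1: VPT.
- Hardly exposed: limb circumference.
- Not exposed: length of stay, major adverse events, weight.

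**3. What share of readings could fall in the acute window?** The plan gives no figure, so this is an assumption. Take a reading at a random time in a 12-hour day, one hour of stimulation in total, *k* sessions without overlap, and a carry-over of *w* hours after each:

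share = (1 + *k* × *w*) / 12

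- *k* = 1: *w* = 0.5 gives 1.5/12 = 12.5%; *w* = 2 gives 3/12 = 25%.
- *k* = 3: *w* = 0.5 gives 2.5/12 = 20.8%; *w* = 2 gives 7/12 = 58.3%.

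**4. What does that do to a test with no sustained effect?** The plan has no power statement, effect size or SD to reproduce. Assumptions: 10 per arm (the 20 hospital subjects split evenly; the protocol states 10 and 10 only for Phase II), coefficient of variation 25%, one two-sample t-test, two-sided alpha 0.05 (Section G2).

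- Standardised shift = rise × share / 0.25
- Noncentrality = shift / √(2/10), with 18 degrees of freedom and critical value 2.101

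Example: a 20% rise at a 58.3% share gives a shift of 0.20 × 0.583 / 0.25 = 0.467 and a noncentrality of 0.467 / 0.447 = 1.04. The chance of p<0.05 is then 16.7%.

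| Transient rise | 12.5% exposed | 20.8% | 25% | 58.3% | 100% |
|---|---|---|---|---|---|
| 10% | 5.1% | 5.4% | 5.5% | 7.8% | 13.5% |
| 20% | 5.5% | 6.4% | 7.1% | 16.7% | 39.5% |
| 30% | 6.2% | 8.3% | 9.7% | 31.7% | 71.8% |

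**5. Check on the approximation.** The formula spreads the rise evenly over the arm. Simulating a true mixture (each reading either has the full rise or none) gives about 16% rather than 16.7% for a 20% rise at 58.3%, and about 28% rather than 31.7% for a 30% rise. The shortcut slightly overstates the larger entries.

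**The case against.** **On-treatment readings are partly the intended target.** The background section hypothesises that stimulation maintains muscle activation and improves perfusion, and thereby prevents or reverses neuromyopathy, so a reading near a session has meaning. That is fair, and pre-session timing is a choice of estimand. But the protocol itself assigns the short-term effect to Aim 1 and effectiveness against neuromyopathy to Aim 2, and untimed readings answer neither cleanly.

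**The two documents describe different designs.** Control group, day 3 and day 9 appear only in the SAP; protocol Phase I is one treated cohort assessed biweekly. This stands, and the passages must be reconciled. The timing gap exists in both versions. A reader might also infer that the SAP analyses oxygenation at days 3 and 9. It does not say so: it names sEMG parameters only for the baseline comparison and otherwise refers to outcome measures generally. Repeated oxygenation as an outcome comes from Section I of the protocol.

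**The large error rates are extreme cases.** This also stands. The 39.5% and 71.8% entries need every reading to fall in the acute window, which would happen only if assessments regularly coincided with sessions. The coefficient of variation and the size of the rise have no source in the documents, and the calculation is one t-test, not the GEE.

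**The data may already exist.** The SAP is written in the past tense. If readings have been taken, new wording cannot retime them. That changes the remedy, not the point.

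**Conclusion.** The point holds for sEMG, tissue oxygenation and Doppler flow, and possibly for dynamometer strength. On these outcomes a group difference or a change from baseline could partly reflect a recent session rather than prevention or treatment of neuromyopathy.

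Under the stated assumptions, a transient 20% rise with no sustained effect lifts the chance of a significant result from 5% to between about 5.5% and 17%, and to about 40% only if all stimulated-arm readings are exposed. This shows how the result depends on timing; it does not estimate the bias, because the acute effect and its washout are not given.

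A reader might infer that all in-hospital outcomes are compromised, or that a device with only a transient effect would be shown to treat neuromyopathy. The documents support neither. Length of stay, adverse events and weight cannot plausibly carry such an effect, and VPT is not among the effects Aim 1 names. The most that follows is that such a device could look effective on sEMG or oxygenation.

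The change should be made: two of three primary outcomes are exposed and the remedy is cheap.

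**What to change.** - In Section F2 (Aim 2), Section I and the SAP, state that sEMG, tissue oxygenation, Doppler and dynamometer readings are taken before any stimulation at baseline, and before that day's first session at each follow-up. Baseline needs the same rule: a post-stimulation baseline set against pre-session follow-up would bias the change the other way.
- Record the clock time of each reading and the minutes since the device last stopped. This needs a stop time added to the therapy chart.
- Use readings taken during or shortly after a session for Aim 1 only.
- Reconcile Section F1, Section I and the SAP on whether the hospital phase has a control group and on the assessment days.
- If data are already collected, run a sensitivity analysis by time since last session, using the therapy log where reading times exist. Where they do not, limit sEMG and oxygenation conclusions to on-treatment effects.

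The cost is wording, one extra chart field and scheduling assessments ahead of the first session. The stimulation schedule does not change and no patients are added. The benefit is conditional: pre-session timing restores the nominal 5% per test only if the acute effect has gone by then. If it has not, the recorded interval at least allows it to be examined.

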Unfortunately, hospital-acquired weakness is highly prevalent among COVID-19 patients, who require paralytics for an extended period of time in order to maintain oxygenation. The prolonged use of these agents lead to long-term inhibition of the Acetylcholine receptors of Neuromuscular junctions. All COVID-19 ventilated patients at our institution have been on paralytics for at least 48 hours, and most of these patients receive concomitant Glucocorticoid therapy. Together Glucocorticoids and paralytics, lead to Myosin depletion and muscle atrophy. This combination has shown to be a risk factor for CINM. In a recent JAMA study on 5700 COVID-19 patients performed in NYC, 72% of the ventilated patients remained in the hospital, and only 3% of this population have been discharged. We believe that the major reason for this is the inability to wean from the ventilator and to rehabilitate due to Neuro-Myopathy.

A recent systematic review suggested the major pathways involved in CINM. These major pathways include muscle disuse due to prolonged immobilization, inflammation, impaired perfusion and oxygen delivery, and hyperglycemia. All these factors might be magnified among COVID-19 patients. Additional to muscle atrophy, a hyper-inflammatory systemic state and coagulation disorders induced by the COVID-19 virus, poor blood oxygen saturation, and poor perfusion to lower extremities are other important risk factors to be aware in these patients. As described above, this type of work may allow physicians to provide more personalized care and evaluate their interventions with a practical test.

Muscle weakness and fatigue impede patients' capacity to exercise, and are known to delay extubation, extend length of stay in hospital, and delay patients to achieve independent mobility. The goal of E-stim in advanced disease states is to prevent or reverse skeletal muscle wasting for persons who are not able to exercise. Conditions include advanced periods of mechanical ventilation.

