Provide a description of your plan for data analysis. State the types of comparisons you plan (e.g. comparison of means, comparison of proportions, regressions, analysis of variance). Which is the PRIMARY comparison/analysis? How will the analyses proposed relate to the primary purposes of your study?

P-values of 0.05 or less will be considered statistically significant based on a two-sided test unless otherwise noted. All variables will be tabulated descriptively at each scheduled time point (baseline and discharge date). For each continuous variable, the analyses will include the mean, standard deviation, minimum and maximum. For each categorical variable, the summary will include frequencies and percentages. Each variable will be analyzed using all available data. Baseline variables will be summarized using descriptive statistics. We assume that a successful intervention is also helpful to maintain subjects muscle mass, reduce neuromyopathy signs and increase venous return flow. The measured parameters (e.g. muscle circumference, sEMG, kent imaging, doppler, etc.) should change substantially from baseline to the end of the intervention. For example, the EMG amplitude values should show increased voltages. Next, for all continuous variables, pre-treatment scores will be regressed on post-treatment scores to form residualized change scores (e.g. sEMG, VPT, dynamometer, etc). Correlations will then be generated among these scores to determine whether changes in sEMG factors are related appropriately with increases in (clinically assessed) functional capacities and self-report measures of activities. ANOVA test will be used to examine significant difference between patients with severe risk factors for prolonged ICU stage (e.g. age, BMI, cardiovascular morbidities). Moderator effects will also be examined for exploratory purposes. Using gender as an example, mixed design ANOVAs will be conducted to determine whether mobility factors change over

the course of treatment at different rates or with different patterns for men and women. Additional analyses will test whether changes in muscle strength and neuropathy (e.g. VPT and dynamometer assessment at time of discharge).

Section H: Potential Risks/Discomforts

H1. Potential Risks/Discomforts

Describe and assess any potential risks/discomforts; (physical, psychological, social, legal, or other) and assess the likelihood and seriousness of such risks:

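### The Protocol does not settle whether hospital length of stay is measured to discharge or only to 4 weeks, and the models it names have no place for stays that are unfinished at 4 weeks

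*Protocol*

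**What the plan says.** Section I (Potential Benefits) of the Protocol names hospital length of stay as a secondary outcome and gives the patient's medical record as its source. The next sentence covers the primary and secondary outcomes together and has them assessed at baseline if feasible and then "on biweekly basis up to 4 weeks or hospital discharge, whichever came first". The sentence after that sets the analysis: "Appropriate mixed models (linear for continuous or Generalized Estimating Equations (GEEs) for non-continuous or non-parametric variables) will be used to test the intervention effect", applied to each primary or secondary outcome. Length of stay is exempted from neither sentence.

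Section F2 (Procedure, Phase I, Aim 2) reads differently. There, "Length of hospital stay and MAE (documented via electronic health record) will be tracked for planning of future studies", with no end date. The 4-week limit in that section belongs to other outcomes: "We will assess incidence of neuropathy and myopathy during hospital discharge or 4 weeks, whichever comes first". Stimulation is to continue for the whole hospital stay.

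Section G2 (Data Analysis) asks for all available data to be used and does not mention unfinished stays. The SAP does not name length of stay. Its GEE compares two groups at baseline, 3 days and 9 days.

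**The concern.** A length of stay is complete only at discharge. A patient still in hospital at 4 weeks has no completed value inside the Section I window. A linear mixed model or GEE has no censoring, so such a stay must either be entered as about 28 days or be treated as missing. No rule says which. Length of stay is also one number per patient, which a repeated-measures model does not fit naturally.

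Unfinished stays are foreseeable. Section C says of a cited COVID-19 series that "72% of the ventilated patients remained in the hospital, and only 3% of this population have been discharged", and attributes this mainly to neuromyopathy, the condition this trial targets.

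Two uses of the result are at stake. Section D hypothesises that stimulation reduces hospital stay, and Section F2 intends the stay data for planning later studies. Capping or dropping the longest stays removes the part of the distribution where a shortening would show most, and dropping them also selects patients on the outcome.

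**Working it through.** **Is there a plan figure to reproduce?** No. Section G1 gives a convenience sample of 40, with no effect size, SD, power or distribution of stay.

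**Inputs**
- Cut-off of 28 days: Protocol Section I, 4 weeks.
- Distribution of stay: assumed log-normal, SD of log stay s = 0.7.
- Effect: assumed 25% shorter median.
- Control median m: assumed, 7 to 40 days.
- Deaths: set aside in these figures.

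**Formulas.** With k = ln(28/m)/s and Φ the standard normal distribution function:
- true mean = m·exp(s²/2)
- share of stays past day 28 = 1 − Φ(k)
- mean if capped = true mean × Φ(k − s) + 28 × (1 − Φ(k))
- mean if dropped = true mean × Φ(k − s) / Φ(k)

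**Worked case, control median 21 days (treated median 15.75)**
- Control: true mean 21 × exp(0.245) = 26.83; k = ln(28/21)/0.7 = 0.411; share past day 28 = 34%. Capped: 26.83 × 0.386 + 28 × 0.3405 = 19.90. Dropped: 26.83 × 0.386 / 0.6595 = 15.72.
- Treated: true mean 15.75 × exp(0.245) = 20.12; k = 0.822; share past day 28 = 21%. Capped: 20.12 × 0.5485 + 28 × 0.2056 = 16.79. Dropped: 20.12 × 0.5485 / 0.7944 = 13.89.
- Differences: true 26.83 − 20.12 = 6.7 days; capped 19.90 − 16.79 = 3.1 days (54% too small); dropped 15.72 − 13.89 = 1.8 days (73% too small).

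**All cases**

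| Control median (days) | Controls past day 28 | True difference (days) | Capped: difference (shortfall) | Dropped: difference (shortfall) |
|---|---|---|---|---|
| 7 | 2% | 2.2 | 2.1 (7%) | 1.8 (20%) |
| 10 | 7% | 3.2 | 2.7 (17%) | 2.0 (37%) |
| 15 | 19% | 4.8 | 3.1 (35%) | 2.0 (58%) |
| 21 | 34% | 6.7 | 3.1 (54%) | 1.8 (73%) |
| 28 | 50% | 8.9 | 2.8 (69%) | 1.6 (82%) |
| 40 | 69% | 12.8 | 2.0 (84%) | 1.3 (90%) |

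The direction does not depend on s = 0.7. With s of 0.6, 0.8 or 1.0 and control medians of 7 to 35 days, 14% to 97% of the true difference is kept if capped and 8% to 90% if dropped. With exponential stays the ranges are 13% to 82% and 3% to 54%.

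**Single-arm reading.** With no control group, the planning mean is what suffers. Taking the 21-day case as the treated cohort, a true mean of 26.8 days would be reported as 19.9 (capped) or 15.7 (dropped).

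**Power.** Simulation with 10 per arm, s = 0.7 and the median halved; control medians 21, 28 and 40 days:

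| Method | 21 | 28 | 40 |
|---|---|---|---|
| t-test, long stays dropped | 28% | 20% | 9% |
| t-test, long stays capped at 28 | 54% | 52% | 45% |
| Log-rank, censored at day 28 | 53% | 52% | 46% |

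Capping shrinks the estimate but costs no material power. The loss comes from dropping. At the 25% shortening, capped t-test and log-rank both have only about 11% to 13%. The 10 per arm is illustrative: the documents state no arm sizes for an inpatient comparison.

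**The case against.** A reader might infer that stay is followed only to 4 weeks and that a benefit is therefore strongly understated. The documents do not support that.

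- **The window.** Both Sections F2 and I take stay from the record, so the true discharge date can be had after week 4. A schedule of baseline plus biweekly assessments describes bedside measurements; stay has no baseline or biweekly value. No passage says that long stays are capped or dropped. This stands: the literal wording of Section I covers stay, but it is not the only reading.
- **The model.** The secondary outcomes that Section I gives as examples for modelling do not include stay, and the SAP does not name it. This stands in part: the models are still assigned to each secondary outcome, and no other method is given for stay.
- **The comparison.** Under Section F1 the whole Phase I inpatient cohort is treated, and the 10 versus 10 groups in Section F2 are Phase II patients treated at home, with no index stay to compare. Only the SAP's control and intervention groups imply an inpatient contrast. This stands.
- **The size.** The 72% and 3% figures concern ventilated patients and come without a follow-up time, so they do not give the share of stays past day 28. Phase I does not require ventilation. With short stays the shrinkage is small. This stands.
- **Power.** A capped mean is a legitimate 28-day restricted mean and tests about as well as log-rank. This stands; the problem there is the name and the interpretation.
- **Deaths.** In-hospital death also ends a stay, has no rule, and can bias in either direction.

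**Conclusion.** The concern holds as an unresolved conflict with a foreseeable consequence. Two analysts following the Protocol could produce different lengths of stay from the same patients, and the only stated analysis cannot represent an unfinished stay. If the Section I window is applied, the mean stay and any between-group difference shrink. Under the log-normal assumptions with s = 0.7 and a 25% shorter median, the difference shrinks by 7% to 84% if capped and 20% to 90% if dropped, for control medians of 7 to 40 days. Where in that range the trial would fall depends on the share of stays past day 28, which the documents do not give. If stay is read from the record to discharge for every patient, the cut-off bias disappears.

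Loss of power follows only from dropping long stays. Bias in a between-group effect is at issue only under the SAP's two-group inpatient comparison. Under the Protocol's single-arm Phase I, the harm is a planning figure that is too short. These figures leave out deaths, so they do not fix the direction of the overall bias.

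**What to change.** In Section I of the Protocol, exempt length of stay from the 4-week limit and state that it is read from the medical record to actual discharge, as Section F2 already allows. Replace the linear mixed/GEE analysis of this outcome, in the Protocol and in the SAP, with time to discharge alive. Report the cumulative incidence of discharge with in-hospital death as a competing event, censor patients still in hospital at data lock, and keep them in the denominator.

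If the 4-week limit is kept, define and report the endpoint as days in hospital within 28 days, not as length of stay, and state how a death before day 28 is counted.

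The cost is wording in both documents and discharge dates taken from records the study already uses. No new procedure or patient is needed. The small downside is that the result becomes a discharge probability, a median or a restricted mean instead of a simple difference in mean days.
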